3.2.2 Secondary efficacy outcome endpoints

3.2.2.1 Proportion of patients alive at 24 months

The proportion of patients alive at 24 months (i.e., OS24) will be defined as the Kaplan-Meier estimate of OS at 24 months. In addition the proportion of patients alive at 12 months (i.e., OS12) will be presented. This will be defined as the Kaplan-Meier estimate of OS at 12 months.

3.2.2.2 Objective response rate

ORR (per RECIST 1.1 as assessed by the BICR) is defined as the number (%) of patients with at least 1 visit response of CR or PR and will be based on a subset of all randomised patients who have measurable disease at baseline per BICR. If the selected reviewer did not consider that a patient has measurable disease then this patient should not contribute to the denominator.

Data obtained up until progression, or the last assessment in the absence of progression, will be included in the assessment of ORR. Patients who go off treatment without progression, receive a subsequent therapy and then respond will not be included as responders in the ORR.

ORR will also be obtained using the algorithm described above for the RECIST site investigator data. The denominator for ORR will be all randomised patients with measurable disease at baseline per the site investigator (ie, the ITT population).

Additionally, ORR will be obtained using the algorithm described above from the RECIST BICR data, but following a modification where any objective progression requires confirmation. Therefore, data obtained up until confirmed progression (ie first progression date that is subsequently confirmed), or the last assessment in the absence of a confirmed progression, will be included in the assessment of ORR. Note that the response may be after an unconfirmed progression.

For exploratory purposes, ORR will also be obtained for the irRECIST 1.1 data provided by BICR.

Best objective response

Best objective response (BoR) is calculated based on the overall visit response from each RECIST assessment. It is the best response a patient has had following randomisation but prior to starting any subsequent cancer therapy and prior to RECIST progression or the last assessment in the absence of RECIST progression and subsequent cancer therapy.

Categorisation of BoR will be based on RECIST using the following response categories: CR, PR, SD, PD and NE.

BoR will be determined programmatically based on RECIST from the overall visit response at each visit using BICR data including all data up until the first progression, the start of any subsequent cancer therapy or the last assessment in the absence of progression.

For determination of a best response of SD, the earliest of the dates contributing towards a particular overall visit assessment will be used. SD should be recorded at least 8 weeks +/- 1 week, i.e. at least 49 days (to allow for the assessment window), after randomisation (i.e. study day 50). For CR/PR, the initial overall visit assessment which showed a response will use the latest of the dates contributing towards a particular overall visit assessment.

The denominator will be consistent with that used in the ORR analysis.

For patients whose PFS event is death, BoR will be calculated based upon all RECIST assessments prior to death.

For patients who die with no RECIST assessments, if the death occurs ≤ 17 weeks (i.e., 16 weeks + 1 week to allow for a late assessment within the assessment window) after randomisation, then BoR will be assigned to the progression (PD) category. For patients who die with no RECIST assessments, if the death occurs > 17 weeks (i.e., 16 weeks + 1 week) after the date of first dose then BoR will be assigned to the NE category.

Progression events that have been censored due to them being more than two missed visits after the last assessment will not contribute to the BoR derivation.

Change in tumour size

For supportive purposes percentage change from baseline in tumour size will be derived at each scheduled tumour assessment visit (i.e., week 8, week 16 etc hereafter referred to as week X for convenience) using BICR data. Best percentage change from baseline in tumour size will also be derived as the biggest decrease or the smallest increase in tumour size from baseline.

This is based on RECIST TL measurements taken at baseline and at the timepoint of interest. Tumour size is defined as the sum of the longest diameters of the TLs based upon RECIST assessments. TLs are measurable tumour lesions. Baseline for RECIST is defined to be the last evaluable assessment prior to randomization. The change in TL tumour size at week X

will be obtained for each patient by taking the difference between the sum of the TLs at week X and the sum of the TLs at baseline. To obtain the percentage change in TL tumour size at week X the change in TL tumour size is divided by the sum of the TLs at baseline and multiplied by 100 (i.e. (week X - baseline) / baseline * 100).

Apply a window around the week X visit: Whenever tumour size data for the week X visit (Note: or visit at which progression was documented if before week X) is available then this should be used in the analysis. A windowing rule will be applied and will follow the protocol allowed visit window; therefore any RECIST scan performed within ± 1 week of the protocol scheduled visit will be used for that visit.

The above derivations will be programmed for the BICR based upon RECIST 1.1 assessments.

Measurements from the reviewer selected by the adjudicator will be used when adjudication for overall visit response has occurred, but in the case where no adjudication was required the measurements from the reviewer who reviewed the baseline scan first will be used for this analysis.

3.2.2.3 Duration of response

DoR (per RECIST 1.1 as assessed by the BICR) will be defined as the time from the date of first documented response until the first date of documented progression or death in the absence of disease progression, whichever is earlier (i.e., date of PFS event or censoring – date of first response + 1). The end of response should coincide with the date of progression or death from any cause used for the RECIST 1.1 PFS endpoint (Section 3.2.1.2). The denominator for DoR related analysis will be defined as described for ORR (see Section 3.2.2.2).

The time of the initial response will be defined as the latest of the dates contributing towards the first visit response of CR or PR.

If a patient does not progress following a response, then the corresponding DoR will be censored at the PFS censoring time.

DoR will not be defined for those patients who do not have documented response.

3.2.2.4 Proportion of patients alive and progression free at 12 months

The proportion of patients alive and progression free at 12 months (i.e., APF12) will be defined as the Kaplan-Meier estimate of PFS at 12 months.

3.2.2.5 Proportion of patients alive and progression free at 18 months

The proportion of patients alive and progression free at 18 months (i.e., APF18) will be defined as the Kaplan-Meier estimate of PFS at 18 months.

3.2.2.6 Time from randomisation to second progression or death (PFS2)

PFS2 will be defined as the time from the date of randomisation to the earlier of the progression event subsequent to that used for the PFS endpoint or death (i.e. date of progression event subsequent to that used for the PFS endpoint or date of death or censoring date whichever is earliest – date of randomisation + 1). The date of the first progression will be programmatically determined from investigator assessed data (See Section 3.1 for details.) The date of second progression will be recorded by the investigator and defined according to local standard clinical practice and may involve any of: objective radiological, symptomatic progression or death. RECIST assessments will not be collected for assessment of PFS2. The date of the PFS2 assessment and investigator opinion of progression status (progressed or non-progressed) at each assessment will be recorded in the electronic case report form (eCRF). Second progression status will be reviewed every 12 weeks following the progression used for the co-primary variable PFS (the first progression) and status recorded. Patients alive and for whom a second disease progression has not been observed should be censored at the last time known to be alive and without a second disease progression, i.e., censored at the latest of the PFS or PFS2 assessment date if the patient has not had a second progression or death.

Time to second subsequent therapy or death (TSST)

As a supportive summary to PFS2, time to start of second subsequent therapy or death (TSST) will be derived. TSST is defined as the time from randomisation to the earlier of the second subsequent cancer therapy start date following study treatment discontinuation, or death (i.e. date of second subsequent cancer therapy/death or censoring – date of randomisation + 1). Any patient not known to have had a second subsequent therapy will be censored at the last date that the patient was known not to have received a second subsequent anti-cancer therapy (obtained from the TTSCAPRX form). If a patient terminated the study for reason other than death before second subsequent therapy, these patients will be censored at the earliest of their last known to be alive and termination dates. Note that the censoring for those patients without a second subsequent therapy will align with their OS.

3.2.2.7 Time to death or distant metastasis

TTDM will be defined as the time from the date of randomisation until the first date of distant metastasis or death in the absence of distant metastasis. Distant metastasis is defined as any new lesion that is outside of the radiation field according to RECIST 1.1 or proven by biopsy. This definition is further refined as patients who enrol in the study have baseline scans performed only after completion of definitive chemoradiation. All known disease must have received a therapeutic dose of radiation prior to protocol entry. For this reason the TTDM endpoint will be determined from recurrent disease that occurs outside of the structures contained within the thorax, including lymph nodes, pulmonary, pleural, and mediastinal metastatic sites and excluding the heart. For the locations of distant metastases, see the Appendix. Patients who have not developed distant metastasis or died at the time of analysis will be censored at the time of the latest date of assessment from their last RECIST 1.1 assessment. However, if the patient has distant metastasis or dies after 2 or more missed visits, the patient will be censored at the time of the latest RECIST 1.1 assessment prior to the

2 missed visits. If the patient has no visits or does not have baseline data they will be censored at Day 1 unless they die within 2 visits of baseline.

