### **11.1.10 Time to death or distant metastasis**

TTDM will be defined as the time from the date of randomisation until the first date of distant metastasis or death in the absence of distant metastasis. Distant metastasis is defined as any new lesion that is outside of the radiation field according to RECIST 1.1 or proven by biopsy. Patients who have not developed distant metastasis or died at the time of analysis will be censored at the time of the latest date of assessment from their last evaluable RECIST 1.1 assessment. However, if the patient has distant metastasis or dies after 2 or more missed visits, the patient will be censored at the time of the latest evaluable RECIST 1.1 assessment prior to the 2 missed visits. If the patient has no evaluable visits or does not have baseline data they will be censored at Day 1 unless they die within 2 visits of baseline.

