3.1.1 Blinded Independent Central Review (BICR) Assessment Using RECIST 1.1

A planned BICR will be carried out using RECIST version 1.1. All radiological scans for all patients (including those at unscheduled visits, or outside visit windows) will be collected on an ongoing basis and sent to an AstraZeneca appointed Contract Research Organisation (CRO) for central analysis. Information prior radiotherapy from the CRF will also be

provided to the BICR to delineate the anatomical region of previous definitive radiotherapy, to confirm that there are no lesions at baseline outside the prior radiotherapy region, to allow the selection of appropriate target lesions, if any at baseline, and to designate new lesions at follow-up that are outside the region of prior radiotherapy as ‘distant’ metastases for derivation of TTDM. The imaging scans will be reviewed by 2 independent radiologists using RECIST 1.1 and will be adjudicated, if required (i.e. two primary reviewers review the scans and adjudication is performed by a separate reviewer in case of a disagreement). The adjudicator must choose the assessments of one of the two primary reviewers. For each patient, the BICR will define the overall visit response (ie, the response obtained overall at each visit by assessing TLs, NTLs and new lesions) data and no programmatic derivation of visit response is necessary. Possible overall visit responses include: for patients with TLs at baseline: CR, PR, SD, PD, not evaluable [NE]; for patients with NTLs at baseline only: CR, non-CR/non-PD (NN), PD or NE; for patients with no disease identified at baseline: PD, no evidence of disease [ND], NE. If a patient has had a tumour assessment that cannot be evaluated then the patient will be assigned a visit response of NE (unless there is evidence of progression in which case the response will be assigned as PD). RECIST assessments/scans contributing towards a particular visit may be performed on different dates and for the central review the date of progression for each reviewer will be provided based on the earliest of the scan dates of the component that triggered the progression.

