4.2.2.7 Time to death or distant metastasis

TTDM will be analysed using identical methods as outlined for the analysis of PFS and adjusting for the same set of covariates, but no subgroup analysis will be performed. Medians and Kaplan-Meier plots will be presented to support the analysis. The sensitivity analysis outlined in Section 4.2.1.2 will not be repeated for TTDM with the exception of a Kaplan Meier plot of the time to censoring where the censoring indicator of TTDM is reversed.

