6. CHANGES OF ANALYSIS FROM PROTOCOL

Table 9 Changes from the planned analysis

Section of SAP Affected (If applicable)	Change	Rationale
4.2.3 Patient Reported Outcomes	Add sensitivity analysis for primary PRO endpoints where RECIST progression counts as an event	To explore the effect of RECIST progression on the PRO endpoint analyses
2.1 Definition of Analysis Sets	Remove criteria that patients need to have post-dose data to be included in the safety analysis set	More widely used definition and to be consistent with other studies
Section 3.2.2.7 Time to death of Distant Metastasis	Clarified definition of Time to death or distant metastasis	Added further detail based on data will be collected
Section 4.2.1.1 Overall Survival	Removed global interaction test for subgroup analyses, subgroups will be tested using model only including treatment	More widely used definition and to be consistent with other studies
Section 4.2.2.1	Remove HR and added p-value to the presentation of OS12	p-value required for multiple testing procedure
Section 4.2.2.4/5	Change presentation of proportion of patients alive and progression free at 12 and 18 months	To match TFL standards
Section 4.2.2.3 Duration of Response	Removed analysis of Duration of Response	Not required
Section 4.2.3.3	Added mixed models repeated measures for analyses of PRO endpoints	To explore the treatment effect using change from baseline data

Section 3.2.1.2, 3.2.2.2, 3.2.2.7	Clarify criteria for censoring in the setting of no progression or death from last evaluable RECIST 1.1 assessment to last RECIST 1.1 assessment	*See below
-----------------------------------	--	------------

*Rationale for the change:

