8. APPENDIX – DETAILS FOR TTDM

The locations of sites of distant metastases are shown in the table below (taken from Appendix 4.7 of the Export Requirements and Technical Specifications per irRECIST 1.1). Locations shown in grey will not be considered distant metastases.

Non-Nodal/New Non-Nodal Target Lesion Location (LESLOC)	Nodal Target/New Nodal Target Lesion Location (LESLOC)	Non-Target/New Lesion Location (NLESLOC)	New Non-Measurable Disease (NMESLOC)	AZ Location	AZ Code
			Liver		160
		Liver - multiple segments - right and left lobes		Liver - Multiple Segments - Right and Left Lobes	1
		Liver - multiple segments - left lobe		Liver - Multiple Segments - Left Lobe	2
		Liver - multiple segments - right lobe		Liver - Multiple Segments - Right Lobe	3
Liver - caudate lobe, segment I		Liver - caudate lobe, segment I		Liver - Caudate Lobe, Segment I	4
Liver - left lobe, segment II		Liver - left lobe, segment II		Liver - Left Lobe, Segment II	5
Liver - left lobe, segment III		Liver - left lobe, segment III		Liver - Left Lobe, Segment III	6
Liver - left lobe, segment IV		Liver - left lobe, segment IV		Liver - Left Lobe, Segment IV	7
Liver - right lobe, segment V		Liver - right lobe, segment V		Liver - Right Lobe, Segment V	8
Liver - right lobe, segment VI		Liver - right lobe, segment VI		Liver - Right Lobe, Segment VI	9
Liver - right lobe, segment VII		Liver - right lobe, segment VII		Liver - Right Lobe, Segment VII	10
Liver - right lobe,		Liver - right lobe, segment		Liver - Right Lobe, Segment VIII	11

segment VIII	VIII			
Liver - left lobe	Liver - left lobe			Liver - Left Lobe
Liver - right lobe	Liver - right lobe			Liver - Right Lobe
Liver - specify	Liver - specify			Liver, Specify
			Lung	
	Lung - multiple lobes bilaterally			Lung - Multiple Lobes Bilaterally
	Lung - multiple lobes left			Lung - Multiple Lobes Left
	Lung - multiple lobes right			Lung - Multiple Lobes Right
Lung - left upper lobe	Lung - left upper lobe			Lung - Left Upper Lobe
Lung - left lower lobe	Lung - left lower lobe			Lung - Left Lower Lobe
Lung - right upper lobe	Lung - right upper lobe			Lung - Right Upper Lobe
Lung - right medial lobe	Lung - right medial lobe			Lung - Right Medial Lobe
Lung - right lower lobe	Lung - right lower lobe			Lung - Right Lower Lobe
Lung - left	Lung - left			Lung - Left
Lung - right	Lung - right			Lung - Right
Lung - specify	Lung - specify			Lung, Specify
			Lymph nodes	
	Lymph nodes - bilateral cervical			Lymph Nodes - Bilateral Cervical

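### SAP 3.2.2.7 limits TTDM to disease outside the thorax, while SAP 3.1.1 and protocol 11.1.10 still count new out-of-field lesions; Section 6 does not say that a class of events is removed

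*SAP*

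**What the plan says.** Protocol 11.1.10 sets a rule based on the radiotherapy field: "Distant metastasis is defined as any new lesion that is outside of the radiation field according to RECIST 1.1 or proven by biopsy". It has no exclusion for the thorax.

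SAP 3.1.1 gives the central reviewers (BICR) information on prior radiotherapy. One stated use is to "designate new lesions at follow-up that are outside the region of prior radiotherapy" as distant, and the sentence ends by saying that this serves the derivation of TTDM.

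SAP 3.2.2.7 opens by repeating the protocol rule and then modifies it: "This definition is further refined as patients who enrol in the study have baseline scans performed only after completion of definitive chemoradiation". It adds that all known disease must have been irradiated before entry, and concludes that "the TTDM endpoint will be determined from recurrent disease that occurs outside of the structures contained within the thorax". The thoracic structures are described as "including lymph nodes, pulmonary, pleural, and mediastinal metastatic sites and excluding the heart". The Appendix implements this with a table of lesion locations and the instruction "Locations shown in grey will not be considered distant metastases".

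SAP Section 6, Table 9, records the change as "Clarified definition of Time to death or distant metastasis". The rationale given is only that further detail was added in view of the data to be collected.

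For the analysis, SAP 4.2.2.7 states: "TTDM will be analysed using identical methods as outlined for the analysis of PFS and adjusting for the same set of covariates". Table 8 specifies a stratified log-rank test on BICR data.

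**The concern.** Two different criteria decide what counts as distant. One asks whether the lesion lies outside the irradiated volume. The other asks whether it lies outside the thorax. They disagree on new lung, pleural and mediastinal lesions that were not irradiated. The BICR is asked to make a designation for TTDM that the TTDM derivation, working from location codes, does not use.

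The event set, event dates, hazard ratio and p-value for TTDM depend on which rule is programmed, and so does the clinical meaning of the result. Under the extrathoracic rule, a patient with new out-of-field lung disease is counted as still free of distant metastasis. A reader who takes the definition from the protocol and the result from an analysis run under the SAP would misread what was estimated. Section 6 would not warn them, because it does not mention that any type of event has been dropped.

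**Working it through.** No arithmetic applies. The documents give no event count, effect size or power for TTDM, so there is no planned figure to reproduce. The check is to take test lesions and classify each under the three passages.

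| New lesion | Protocol 11.1.10 | SAP 3.1.1 (BICR label) | SAP 3.2.2.7 operative rule |
|---|---|---|---|
| Liver, outside field | Event | Distant | Event |
| Contralateral lung, outside field | Event | Distant | Not an event |
| Pleura, outside field | Event | Distant | Not an event |
| Lung, inside field, no biopsy | Not an event | Not distant | Not an event |
| Heart, inside field, no biopsy | Not an event | Not distant | Event, on the natural reading |

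**Rows 2 and 3** are the conflict. The last column follows from the sentence in 3.2.2.7, which names pulmonary and pleural sites among the thoracic structures. It does not rest on the Appendix shading, which is not visible in the text available for this review. That loss is no fault of the plan.

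**Row 5** shows that the rules are not simply nested. If the heart is taken out of the thoracic structures, a heart lesion can count under the SAP rule without being out of field. The clause is awkwardly worded, so this is a reading and not a certainty.

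**Effect on one patient.** Suppose that the only new disease is an out-of-field lung lesion.
- Under the protocol rule, TTDM ends with an event at that scan.
- Under the SAP rule, the patient continues event-free. Protocol 6.3 requires scheduled scans only until confirmed progression (unless study drug continues) and makes scans optional for patients who then stop study drug. SAP 3.2.2.7 censors at the last RECIST assessment if there is no event, and also censors a death that follows two or more missed visits.
- The narrower rule can therefore replace an event with censoring at about the time of progression, as well as delay an event. In-field progression already has this feature under either rule. The extrathoracic rule extends it to out-of-field intrathoracic spread.

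**Order of changes.** The SAP amendment history dates the TTDM refinement and the Appendix table to 5 December 2016. That entry names Section 3.2.2.7 and the Appendix but not 3.1.1. The SAP of 22 March 2017 carries both rules, and the protocol of 4 September 2019 carries the field rule. This fits a refinement that was not carried through to the related text.

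**The case against.** The strongest reply is that the operative rule can be identified. SAP 3.2.2.7 says openly that it refines the protocol definition, gives a reason, says what the endpoint will be determined from, and supplies a code list. A programmer following that section would not be choosing freely. This stands. The opening sentence of 3.2.2.7 should not be counted as a separate competing definition, and the extrathoracic rule should be taken as the SAP's intent.

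Second, the change is disclosed in part, in the amendment history and in Section 6. This also stands, and a reader should not infer concealment. But the entry describes a clarification and does not say that lesions the protocol counts have ceased to count.

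Third, SAP 3.1.1 speaks of an anatomical region of prior radiotherapy and not of a field, and in Stage III lung cancer that region might be read as the thorax. This is strained: the sentence uses radiotherapy information from the CRF to delineate the region, which would be unnecessary if the region were always the whole thorax. Even if accepted, it would leave protocol 11.1.10 in conflict with SAP 3.2.2.7.

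Fourth, the 2019 protocol states that the endpoints had been met and the planned analyses concluded, so text carried over in 11.1.10 does not show that the SAP rule was withdrawn. Agreed. It shows only that the two documents were not aligned.

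Fifth, TTDM is outside the multiple testing procedure, and new intrathoracic lesions remain progression events for PFS. Both are true, and they limit the consequences.

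**Conclusion.** The passages conflict as written and should be reconciled. A new lung or pleural lesion outside the field is an event under protocol 11.1.10 and is labelled distant for TTDM under SAP 3.1.1, but it is not an event under SAP 3.2.2.7. Section 6 does not state that these events are removed. The conclusion rests on the natural reading of the list of thoracic structures in 3.2.2.7.

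The consequence is confined to TTDM. SAP 4.1.2 limits the multiple testing procedure to PFS, OS, OS24 and ORR, so alpha control, power and the co-primary results do not change.

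Two stronger readings are tempting. A reader might infer a number of misclassified patients by applying assumed fractions to the planned 458 PFS events. The documents give neither the share of progressions with a new lesion nor the share that are out of field but only intrathoracic, so no count can be supported. Some of those patients would in any case become TTDM events later. A reader might also infer that the extrathoracic rule is wrong and the field rule must be restored as the main analysis. The SAP's reason, that known disease was already irradiated, does not by itself explain leaving out unirradiated lung lesions. But nothing in the documents shows that classification by field is the more reliable of the two, and either could be defended if it were used consistently.

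**What to change.** Use one TTDM definition throughout.

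1. If the extrathoracic rule is kept, align SAP 3.1.1 and protocol 11.1.10 with it. In 3.1.1, say that the BICR's field-based designation feeds the sensitivity analysis in item 3. State plainly in 3.2.2.7 whether a heart lesion counts.
2. In SAP Section 6, replace the clarification entry with a statement that new intrathoracic lesions outside the radiation field are no longer TTDM events, described as a change from the protocol and with the reason.
3. Report TTDM under the protocol's field-based definition as a named sensitivity analysis, using the designation that 3.1.1 already plans, with the same stratified log-rank test and hazard ratio.

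The cost is wording changes in the two documents and one extra derivation and analysis. The plan already calls for both the field-based designations and the location codes, so no new data collection is needed.
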